## RESEARCH DESIGN AND METHODS (see Schema)

### Patient Selection

**Inclusion Criteria:** Adult patients meeting International Classification of Headache Disorders 3rd Edition (ICHD-3) criteria for a diagnosis of SIH (Table 1) who have had a contrast-enhanced brain MRI and a myelogram confirming the presence of a CSF leak will be recruited from the Duke Radiology spine intervention clinic [25].

[figure not shown]
**Exclusion Criteria:** (a) recent (i.e., < 2 weeks) blood patch, (b) contraindication or inability to undergo the procedure, (c) inability to provide informed consent, (d) expected inability to complete follow-up assessment, (e) a contraindication to receiving contrast material (precluding an epidurogram), or (f) contraindication to receiving fibrin glue (i.e., allergy). We aim to recruit 148 patients over 2 years. This number is based on the historical number of patients with SIH and confirmed CSF leaks treated at Duke, our sample size determination (see *Statistics*), and previously published studies.

A) Any headache fulfilling criterion C
B) Headache has developed in temporal relation to the low CSF pressure or CSF leakage, or has led to its discovery
C) Headache has developed in temporal relation to the low CSF pressure or CSF leakage, or has led to its discovery

### CT Fluoroscopy-Guided Blood and Fibrin Glue Patching

We will employ a single-center, parallel, randomized, blinded, prospective design. Enrolled patients will be assigned to one of two treatment arms using a block randomization scheme: CT fluoroscopy-guided blood and fibrin glue patching targeted to the site of CSF leak or a simulated procedure without patching material. Baseline data will be collected including: (a) symptom profile and duration, (b) headache impact test (HIT-6), (c) EQ-5D (a measure of overall health status), and (d) work productivity and activity impairment (WPAI) (see *Outcomes*). All procedures will be performed under CT fluoroscopy on the same scanner (see *Resources*). The location of injection for patients in both arms will be targeted to the site of the CSF leak identified on prior imaging (e.g., CT or dynamic myelogram). All procedures will be performed by a board-certified radiologist with a CAQ in neuroradiology and at least six years of experience in CT fluoroscopy-guided spine injections.

Patients in both arms of the study will be placed supine on the CT gantry table. Intravenous (IV) access will be obtained and sterile autologous blood will be acquired for the purposes of possible patching. A planning CT scan (120 kVp, automatic tube current modulation: 100 – 400 mA, 2.5 mm section thickness, gantry rotation time 0.5 seconds) will be obtained with z-axis limited to the area of interest. Acquired images will be used to plan a needle trajectory and approach to the location of the CSF leak for targeted patching using previously described techniques for CT fluoroscopy-guided epidural patching (e.g. a lateral approach trajectory to the neuroforaminal epidural space, an oblique interlaminar trajectory to the dorsal spinal canal epidural space, or an approach traversing the neuroforamen to reach the ventral epidural space) [14, 26-29]. The skin surface will then be marked, sterilized, draped, and anesthetized with 2% lidocaine. At this point, a computer generated randomized treatment assignment will be delivered to the treating physician in an opaque sealed envelope, which will determine if the patient is treated with targeted blood and fibrin glue patching versus the simulated procedure. Patients and outcome assessors will remain blinded to the treatment assignment throughout the study. The treating physicians are unable to be blinded, as

they will be aware of the type of patching material used. The effectiveness of patient blinding will be assessed using the Bang Blinding Index prior to discharge on the day of the procedure [30].

**Targeted Patching of CSF Leaks with Blood and Fibrin Glue (Experimental Arm)**

For patients randomized to targeted patching with blood and fibrin glue, a 22-gauge 3.5 or 5 inch Quincke tip spinal needle will be advanced under intermittent CT fluoroscopic-guidance to the epidural space at the target location. On reaching the target, gentle aspiration will confirm absence of blood return. Approximately 0.2 mL of contrast material (iopamidol 200 mgI/mL; Isovue-M 200, Bracco Diagnostics Inc., Princeton, NJ) will then be injected to assess needle tip position and potential future spread of patching material. Intravascular injection will be excluded using a “double-tap” technique (i.e., 2 sets of CT fluoroscopic images: an initial image immediately after injection and a second image acquired 2-3 seconds later to assess for contrast material washout), as previously described [31]. After visual confirmation of correct needle tip position, a mixture of autologous blood (~1 mL) and fibrin glue (~1-3 mL) will be slowly injected. This process will be repeated for all planned needle placements. The number of needle placements and total volume of blood and fibrin glue will be at the discretion of the treating radiologist, but will be based upon: (a) the extent of spread of patching material, (b) mass effect on the thecal sac and neural structures, and (c) patient symptoms. On completion of the procedure, the patient will be observed for 2 hours in the radiology post-procedural unit.

**Simulated Patching Procedure (Control Arm)**

[figure not shown]
Patients randomized to undergo the simulated patching procedure will have the same experience as the patients in the experimental arm, as described above. This includes placement of an IV, acquisition of sterile blood for potential autologous patching (which will be discarded rather than used), a planning CT, all of the same needle placements that would have been performed if the patient were randomized to the experimental arm, and contrast injection for the epidurogram. However, instead of injection of blood and fibrin glue patching material through the needles, an equivalent volume of preservative free sterile saline will be injected (buffered intrathecal electrolyte/dextrose injection; Elliotts B Solution, Lukare Medical, Scotch Plains, NJ). On completion of the procedure, the patient will be observed for 2 hours in the post-procedural unit.

**Adverse Events**

Patients will be screened for adverse events immediately after the procedure as well as via phone call at one week post-procedure.

While all adverse events will be recorded, the following will be considered major adverse events: stroke, paralysis, or other permanent neurologic deficit; allergic reaction; hospitalization or ED visit. Minor adverse events will include, but not be limited to: nausea and/or vomiting, symptomatic hypertension, vasovagal reaction, temporary weakness or sensory deficit, and urinary retention.

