**Statistics**

**Patient Outcome Analysis**

The change in HIT-6 from a pre-procedural score of > 56 (substantial or severe impact on life) will be considered for each group at each time point. *Primary Endpoint (HIT-6 at 1 month)*: We will apply a two-sample t test, or in the cases of low counts and non-parametric data a Wilcoxon Rank Sum test, to test the primary endpoint. *Secondary Endpoints*: The same analysis will be employed for all secondary endpoints at each time point.

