#### Interim Data Analysis

An interim analysis will be performed of the first 74 patients by the biostatistician. All study participants and other personnel will remain blinded. Safety and efficacy will be evaluated using an O'Brien–Fleming stopping rule of  $p < 0.001$  in order to evaluate for early evidence of treatment efficacy [43].

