#### Crossover, Withdrawal, or Missing Data

We will employ an intention-to-treat (ITT) analysis for this trial [44]. Patients that crossover between study arms, withdraw from the study, or for whom there is missing data will all be handled in the same manner: we will conservatively assume that no further benefit will be gained from the initial treatment. As such, the most recent available outcomes data will be extrapolated to all later time points for which no data are available.

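### The stated adverse-event screenings, on the procedure day and at one week, cannot show whether a remaining deficit is permanent and do not systematically capture later hospital or emergency visits

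*Combined protocol and SAP*

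**What the plan says.** The Adverse Events section of the combined protocol and SAP sets two screenings: "Patients will be screened for adverse events immediately after the procedure as well as via phone call at one week post-procedure". It goes on: "While all adverse events will be recorded, the following will be considered major adverse events", and the major list is "stroke, paralysis, or other permanent neurologic deficit; allergic reaction; hospitalization or ED visit". The minor list includes "temporary weakness or sensory deficit, and urinary retention". The section gives no duration that separates permanent from temporary, no reporting period, and no rule for an event still open at the call.

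Outcome measurement runs longer. Patient Outcome Analysis places the primary endpoint, HIT-6, at 1 month and says of the rest: "The same analysis will be employed for all secondary endpoints at each time point". The section on crossover, withdrawal and missing data says that "the most recent available outcomes data will be extrapolated to all later time points for which no data are available", so further assessments are planned. Crossover to the other arm is allowed at two months. Interim Data Analysis, on the first 74 patients, says that "Safety and efficacy will be evaluated".

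The Timeline of Events heading has no readable content, and the list of outcome time points is not readable elsewhere.

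**The concern.** The major or minor label for some neurologic deficits depends on how long they last, but the last stated screening is at one week. That is too early to call a persisting deficit permanent, and no later check is stated that would settle it.

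Admissions and emergency visits are major with no time window, yet patients are asked about them only up to day 7. Later ones rely on spontaneous report, which need not be equally complete in the two arms. The readable text also does not say whether the screenings are repeated after a crossover procedure.

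At stake is the major-event count for an invasive spinal procedure, both in the final safety statement and in the safety part of the interim review.

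**Working it through.** The plan gives no adverse-event rate or safety calculation to reproduce. The main check sets the definitions against the schedule; the arithmetic that follows only gives scale.

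**1. What the two screenings can classify**

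| Event | Class available from the stated screenings |
|---|---|
| Stroke or paralysis found by the one-week call | Major, named outright |
| Deficit leading to an admission or emergency visit by the one-week call | Major, through that visit |
| Weakness or sensory loss resolved by the call | Minor, temporary |
| Deficit still open at the call, no other major criterion | Not classifiable |
| Admission or emergency visit after day 7 | Major, but not asked about |

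The gap lies in the last two rows. The fourth row needs a definition of permanent and a later observation; the readable text gives neither.

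**2. How much of the follow-up is screened**

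Inputs: last screening at day 7, primary endpoint at 1 month (taken as 30 days), crossover at two months (taken as 60 days).

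- To the primary endpoint: 7/30 = 0.233, about 23%.
- To the crossover point: 7/60 = 0.117, about 12%.

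**3. Illustration of incomplete capture**

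The 74 patients per arm come from Sample Size Determination. The true risk p and the captured share s are assumptions, because the documents give neither.

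P(at least one event seen) = 1 − (1 − p·s)^74

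For p = 0.02 and s = 0.5 this is 1 − 0.99^74 = 0.525.

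| Captured share s | p = 1% | p = 2% |
|---|---|---|
| 1.00 | 0.525 | 0.776 |
| 0.75 | 0.427 | 0.673 |
| 0.50 | 0.310 | 0.525 |
| 0.25 | 0.169 | 0.310 |

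The rows 0.50 and 0.25 correspond to half and three quarters of events arising after day 7 with none of them reported. If a share e arises by day 7 and a fraction r of the later events is volunteered, then s = e + (1 − e)·r. With e = 0.5 and r = 0.5, s = 0.5 + 0.5 × 0.5 = 0.75, so partial spontaneous reporting recovers part of the loss.

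**4. The same at the interim**

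Assume about 37 of the first 74 patients were patched (74/2). For p = 0.02 the results are:

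- s = 1: 1 − 0.98^37 = 0.53
- s = 0.5: 1 − 0.99^37 = 0.31
- s = 0.25: 1 − 0.995^37 = 0.17

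**The case against.** The strongest objection is that the timeline content cannot be read and may list later checks. The Adverse Events section names two screening times; it does not call the second the last one or close the reporting period. A reader might infer that safety reporting ends at one week. The documents do not support that. What stands is that the section devoted to adverse events states no later questioning, and it should agree with whatever the timeline shows. Its silence on what permanent means does not depend on the timeline.

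A reader might also infer that events after day 7 leave no trace. That goes too far, because the commitment to record every adverse event carries no time limit and covers volunteered reports. But volunteered reports are not the same as asking both arms the same questions at the same times.

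A third tempting reading is that neurologic events in general cannot be classified. Stroke and paralysis are named as major, and a deficit that leads to an admission or emergency visit is major by that route. Nor must a deficit be classified on day 7. Only the remaining group is affected, and for it no later observation is stated.

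The detection probabilities have no source in the documents, and the two lowest rows assume that no late event is reported. That objection stands in full: they are illustrations.

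It is also fair that contact beyond 1 month is inferred, and that the mode of contact is not readable. If questionnaires are self-completed, the added work is greater than a few extra spoken questions.

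Finally, late admissions and emergency visits may reflect persisting disease. The plan assumes 50% response with patching and 30% with the simulated procedure, so 50% and 70% would remain without response. Pooling all late visits as procedural harm could make patching look safer than it is. This is a sound reason to show early and late events apart, but not a reason to leave late events uncollected.

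**Conclusion.** The concern holds in a limited form. On the readable text, a deficit still open at one week with no other major criterion cannot be classified from the stated screenings, and later admissions and emergency visits are not systematically captured. This follows from the wording alone and needs no assumed rate. How many patients it would affect cannot be derived from the documents.

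For scale only: the stated screening covers about 23% of the time to the primary endpoint. At an assumed 2% risk in 74 patched patients, the chance of seeing at least one event would be 78% with full capture, 53% with half captured and 31% with a quarter captured. At 1% the figures are 53%, 31% and 17%.

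The interim review would work from the same incomplete count. A reader might infer that a safety stopping decision is compromised. The documents do not show that: the stopping rule's stated aim is early evidence of efficacy, and no rule based on adverse-event counts is given.

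The conclusion would narrow if the timeline lists later checks. Reconciling the two places and defining permanent would still be needed.

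**What to change.** Amend the Adverse Events section as follows:

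- Ask the same adverse-event questions in both arms at the 1-month primary-endpoint contact and at each later planned outcome contact, and apply the screening schedule after any crossover procedure.
- Follow every deficit open at one week to resolution or last contact, and state in advance how permanent is determined.
- State the period over which admissions and emergency visits are counted.
- Record relatedness for each event, so that persisting disease is not read as procedural harm. Since treating physicians know the assignment, a blinded assessor would be the natural choice.
- Tabulate events by randomised arm and by procedure received, showing events through day 7, later events and post-crossover events separately.
- If the timeline already lists later checks, bring the section into line with it.

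The cost is one revised paragraph, one safety table and somewhat more data collection at planned contacts, with more effort if those are self-completed. More unrelated background events will be recorded, and their rate may differ by arm. The separate tabulation and the relatedness field are there to handle that. The sample size and the efficacy analysis do not change.

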**Timeline of Events**

**Patient Outcome Measures and Crossover**

**Headache Impact Test (HIT-6):** A validated headache assessment tool with good internal consistency and test-retest reliability that is designed to provide a global measure of headache impact in six domains [32]. Scores range from 36 (asymptomatic) to 78 (severe headache). Score ranges: 36-49 (little or no headache impact), 50-55 (some impact), 56-59 (substantial impact), and >60 (severe impact) [33, 34]. Prior studies have determined that the minimally important clinical difference between groups is 1.5 points for the HIT-6 [35].

**EQ-5D:** A standardized measure of health status that provides a simple, generic measure of health for clinical appraisal [36]. It is well-validated for health status measurement [37] and for quality-of-life in headache [34].

**Patient Global Impression of Change (PGIC):** A validated 7-point Likert-type scale assessing a patient’s overall impression of improvement after intervention [38, 39].

**Work Productivity and Activity Impairment (WPAI):** A validated instrument with good test-retest reliability used extensively in health research [40, 41] that quantifies impairment in daily activities and work productivity [42].

**Crossover:** Patients will be permitted to crossover to the other treatment arm two months after the procedure.

**Statistics**

**Patient Outcome Analysis**

The change in HIT-6 from a pre-procedural score of > 56 (substantial or severe impact on life) will be considered for each group at each time point. *Primary Endpoint (HIT-6 at 1 month)*: We will apply a two-sample t test, or in the cases of low counts and non-parametric data a Wilcoxon Rank Sum test, to test the primary endpoint. *Secondary Endpoints*: The same analysis will be employed for all secondary endpoints at each time point.

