#### Sample Size Determination

Based on previously acquired prospective outcomes data (unpublished), we will conservatively estimate a positive response rate of 50% in our experimental arm (see *Preliminary Studies*). In a meta-analysis examining sham procedures, our group found a maximum placebo response of 30% ([name], unpublished). Therefore, to obtain a power of 0.8 (alpha 0.05) to detect superiority of the blood and fibrin glue patching group, assuming positive response rates of 50% for the patching group and 30% for the control group, we would need a total of 148 patients (74 patients in each arm).

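### The primary HIT-6 test has no baseline adjustment and does not state whether the 1-month score or its change is tested; ANCOVA on the baseline already collected settles both

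*Combined protocol and SAP*

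**What the plan says.** The whole primary analysis is in Statistics, Patient Outcome Analysis. It opens: "The change in HIT-6 from a pre-procedural score of > 56 (substantial or severe impact on life) will be considered for each group". The endpoint label that follows is "Primary Endpoint (HIT-6 at 1 month", and the test is given as: "We will apply a two-sample t test, or in the cases of low counts and non-parametric data a Wilcoxon Rank Sum test". For the rest: "The same analysis will be employed for all secondary endpoints at each time point". Neither a covariate nor a baseline-adjusted model is mentioned anywhere in the document.

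The baseline values will exist. The section on CT fluoroscopy-guided patching says "Baseline data will be collected including: (a) symptom profile and duration, (b) headache impact test (HIT-6" and continues with "c) EQ-5D (a measure of overall health status), and (d) work productivity and activity impairment (WPAI".

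The Sample Size Determination section does not resolve which HIT-6 variable is meant, because it works from responder proportions: "assuming positive response rates of 50% for the patching group and 30% for the control group".

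**The concern.** Two things are left open in the primary test. The variable may be the 1-month score or the change from baseline. The method may be a t test or a Wilcoxon test, with no stated trigger for switching. That makes up to four versions of the primary comparison, and the choice could be made after data have been seen. The Interim Data Analysis section plans an efficacy look at the first 74 patients, so the choice matters before the end of the trial.

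The choice of variable is not neutral. For the same true effect, score and change can have quite different power. Which is better depends on the correlation between baseline and 1 month and on the ratio of the two standard deviations, neither of which the documents give. A model with baseline as covariate removes the need to guess and uses information the trial collects anyway. Because the same analysis is carried to the secondary endpoints, the gap extends to EQ-5D and WPAI.

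**Working it through.** **The plan's own figure.** The stated total is 148 (74 per arm) for 50% against 30% response, power 0.8, alpha 0.05. The pooled-variance formula is n = [z(alpha)·√(2·p̄·(1−p̄)) + z(power)·√(p1(1−p1) + p2(1−p2))]² / (p1−p2)², with p̄ = 0.40.

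- One-sided alpha: (1.645·0.693 + 0.842·0.678)² / 0.04 = 73.1, so 74 per arm and 148 in total. This matches.
- Two-sided alpha: 93 per arm, 186 in total.

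The stated number therefore reproduces with a one-sided 0.05 and concerns proportions. It carries no HIT-6 standard deviation and cannot show which HIT-6 variable is tested.

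**Inputs for the comparison.** From the documents: 74 per arm and alpha 0.05. Assumed: two-sided testing; r, the within-arm correlation of baseline and 1-month HIT-6, at 0.3, 0.5 and 0.6; k, the baseline SD divided by the 1-month SD, at 1.0, 0.7 and 0.5. The interim look is ignored.

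**Variance of the treatment effect, relative to the score test.**

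- Score at 1 month: 1
- Change: 1 + k² − 2rk
- ANCOVA: 1 − r², whatever k is

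Subtracting, change minus ANCOVA is (k − r)² and score minus ANCOVA is r². Neither can be negative, so in large samples ANCOVA is at least as precise as either test. It ties with change only when k = r and with the score only when r = 0. Its cost is one degree of freedom (145 instead of 146).

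**Power.** An effect of d = 0.4636 one-month SDs has noncentrality 0.4636·√(74/2) = 2.82 and gives the score t test 80% power. Dividing 2.82 by the square root of each relative variance and using the noncentral t distribution gives:

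| Test | r = 0.3: variance, power | r = 0.5: variance, power | r = 0.6: variance, power |
|---|---|---|---|
| Score | 1.00, 80% | 1.00, 80% | 1.00, 80% |
| Change, k = 1.0 | 1.40, 66% | 1.00, 80% | 0.80, 88% |
| Change, k = 0.7 | 1.07, 77% | 0.79, 88% | 0.65, 93.5% |
| Change, k = 0.5 | 0.95, 82% | 0.75, 90% | 0.65, 93.5% |
| ANCOVA | 0.91, 84% | 0.75, 90% | 0.64, 94% |

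ANCOVA's gain in percentage points, from unrounded powers, is:

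- over the score: 4, 10, 14
- over change, k = 1.0: 18, 10, 6
- over change, k = 0.7: 6, 2, 0
- over change, k = 0.5: 2, 0, 0

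In score-test terms, 148 patients analysed by ANCOVA are worth 148/(1 − r²) = 163, 197 and 231.

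A value of k below 1 is plausible. The outcome sections say "Scores range from 36 (asymptomatic) to 78 (severe headache", while the analysis section describes baselines above 56, which would confine them to the upper part of that range.

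**Simulation check.** With 20,000 trials per cell, simulated power agreed with these values to within about one point. Rejection under the null (8,000 trials per cell) was 0.045 to 0.053 for all three tests.

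**Why ANCOVA settles the variable.** If Y1 = a + b·arm + c·Y0, then Y1 − Y0 = a + b·arm + (c − 1)·Y0. The treatment coefficient b, its standard error and its p value are the same for score and for change.

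**The case against.** The best counter-argument is that change is the natural reading. The section opens with change, and the later label may only name the instrument and the time point. On that reading, with the baseline SD smaller than the 1-month SD, the gain is 6 points at most in the grid above and often nothing. One added word would then remove the ambiguity without a new model. This stands as a limit on the size of the gain. It does not remove the point: a primary test should not rest on inference, and nobody can know in advance that k will lie close to r.

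The assumed correlations can also be challenged. At r = 0.2 ANCOVA reaches only 81.6% against 80% for the score, and at r = 0.1 only 80.4%. If baselines are restricted to above 56, r would tend to be low. This too is fair, so 4 to 14 points over the score is not a bound. But low correlation is also where change does badly: at k = 0.5 its power is 78% at r = 0.2 and 74% at r = 0.1. Using a one-sided alpha, as the stated sample size implies, brings the gains over the score to about 3, 9 and 13 points, which alters little.

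No power was computed for the Wilcoxon branch, and the Schema, which is not shown, might say more about the variable or the threshold. Finally, ANCOVA does not resolve the separate mismatch between a trial sized on responder rates and a test on a HIT-6 score.

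**Conclusion.** The point holds. The plan specifies no baseline adjustment, does not state outright whether score or change is tested, and leaves the switch to the Wilcoxon test without a criterion, although the needed covariate is collected. This is a matter of specification and precision, not of bias: the planned tests are valid under randomisation.

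The size is illustrative, since r and k are assumed. If the score is the planned variable, ANCOVA adds 4 to 14 points of power for r from 0.3 to 0.6, and less below that. If change is planned, the gain runs from 18 points (r = 0.3, equal SDs) to about nil (k near r). Apart from one degree of freedom, ANCOVA gives nothing away in large samples with equal arms. The change is worth making; confidence in the size of the benefit is moderate.

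**What to change.** State one primary analysis in Patient Outcome Analysis: ANCOVA of 1-month HIT-6 on randomised arm with baseline HIT-6 as covariate, in all randomised patients as assigned, reporting the adjusted mean difference with its 95% confidence interval. Run the Wilcoxon test as a sensitivity analysis in every case, whatever the distribution looks like. Settle this before the interim analysis.

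Use the same model for EQ-5D and WPAI, each with its own baseline. PGIC has no baseline and should stay a two-group comparison.

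As a clarification, define the role of the > 56 threshold. The inclusion criteria in Patient Selection state no HIT-6 minimum, and the section on crossover, withdrawal and missing data declares intention-to-treat, so the text should confirm that every randomised patient enters the primary analysis.

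The cost is SAP wording only: no extra patients, visits or data, and one degree of freedom in the model.
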